**Either predose<15ng/ml plus 4h<600ng/ml OR SHBG<+75%CFB.

No titrations will be made based on TSH which has not changed in the Main Study. TSH will be unblinded in the Extension Study. Downtitrations have not been needed for changes in FT4, but the same downtitration rules will apply in the Extension Study.

At the Extension Study Week 12 Visit, patients will have an MRI-PDFF. Within 10 days prior to or at the Extension Study Week 36 visit while the patient is still on treatment another MRI-PDFF will be performed. If available, a fibroscan may be performed at the Extension Study Week 36 visit.

DSMB

A Data Safety Monitoring Board (DSMB) will oversee the study to ensure patient safety and to advise if any dosing alterations are recommended. The DSMB will review safety including thyroid hormone effects, liver-related events (ie, clinically meaningful elevations in liver enzymes ALT, AST, and bilirubin), cardiovascular assessment (ie, changes in ECG, cardiac biomarkers, cardiac AEs, cardiac symptoms, arrhythmias, etc.), SAEs for trends in causality, and other efficacy (lipid parameters) and safety data as needed. The DSMB will perform regularly scheduled reviews the first scheduled for when 25 patients have received 6 weeks of treatment. Additional regularly timed meetings will be held and ad hoc meetings may also occur if determined by Madrigal and the DSMB.

DOSAGE FORMS AND ROUTE OF ADMINISTRATION:

MGL-3196 and matching placebo are available as hard gelatin capsules for oral administration in 40 mg and 60 mg strengths. Patients will be randomized to 1 of 2 treatments: MGL-3196 80 mg or placebo given orally once-daily in the morning for 36 weeks. Each patient will receive study drug bottles labeled as A and B. Patients will take 1 capsule from bottle A and 1 capsule from bottle B at each dosing. Each bottle will contain 32 capsules (64 capsules total), enough for 4 weeks + 4 days of dosing. Based on PK assessments and/or thyroid hormone results, the dose may be adjusted between 40 and 100 mg in intervals of 20 mg. The patient, study personnel, and Sponsor will remain blinded throughout the study.

EFFICACY VARIABLES:

The primary efficacy variable is percent change in hepatic fat fraction by MRI-PDFF from baseline at 12 weeks for MGL-3196 80 mg versus placebo.

The secondary efficacy variables include the following:

- The number and percentage of patients achieving a 2-point reduction in NAS at 36 weeks for MGL-3196 80 mg versus placebo;

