3.1.2 Treatment Period

Following randomization, patients will begin the initial 12-week Treatment Period. Patients will undergo liver MRI-PDFF prior to the start of treatment (pre-dose), at the end of the initial 12-week Treatment Period (12 weeks after the start of treatment), and after continuing blinded treatment (MGL-3196 or placebo) for an additional 24 weeks (36 weeks after the start of treatment). A liver biopsy will be obtained prior to start of treatment (pre-dose) if the patient has not had a qualifying liver biopsy within 180 days of randomization and at 36 weeks. During the study, patients will return to the study site periodically for assessment of vital signs (temperature, pulse, respiratory rate, and seated blood pressure), 12-lead electrocardiogram (ECG), and clinical laboratory testing (hematology, chemistry, and urinalysis). During the study, patients who need to be placed on any excluded lipid lowering therapeutics will be discontinued from the study. Blood samples will be collected at specified times for the assessment of lipid parameters, thyroid hormone parameters, and other biomarkers. Patients will be evaluated for adverse events and concomitant medication use throughout the study. Patients should be monitored throughout the study for clinical signs and symptoms of hyper- or hypothyroidism.

A PK assessment will be made at Week 2 including a pre-dose fasting determination and assessments at 2, 4, 6, and 8 hours postdose. As described in PK section, patients who have a calculated $AUC_{inf} \leq 5500 \text{ ng*hr/ml}$ (combined MGL-3196 and MGL-3196-M1) will continue on 80 mg. For patients (~ 10%) with an $AUC_{inf} \leq 3000 \text{ ng*hr/ml}$ as described in Section 8 who are predicted to have exposure at 100 mg that remains $AUC \leq 5550$ based on a conservative calculation, the MGL-3196 dose will be increased from 80 mg to 100 mg at the Week 4 visit. For patients with combined $AUC > 5500 \text{ ng*hr/ml}$, the dose of MGL-3196 will be reduced to 60 mg per day on the Week 4 visit. Patients with $AUC_{inf} > 11,000$ (combined MGL-3196 and M1) plus $SHBG > 150\%$ increase from baseline at Week 2 (indicative that average or steady-state exposure is $> 11,000 \text{ ng*hr/ml}$) will be downtitrated to 40 mg at Week 4. If $SHBG \leq 150\%$, then patient will be downtitrated to 60 mg at Week 4, and patient's Week 4 SHBG and predose concentrations will be evaluated. If at Week 4 $SHBG > 150\%$ increase from baseline and predose

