>40ng/ml for MGL-3196 and >40ng/ml for M1 then patient will be downtitrated to 40 mg at the Week 8 visit.

A combined MGL-3196 and MGL-3196-M1 exposure \leq 5500 ng*hr/ml has not demonstrated a drug-related decrease in FT4 to $<$ LLN $<$ 0.7 ng/dL in Phase 1 studies. However, patients with NASH without symptoms of hypothyroidism may occasionally have low baseline levels of FT4, with normal FT3 and TSH, and are not clinically or subclinically hypothyroid. Low FT4 in the presence of normal FT3 (active hormone) and TSH is not consistent with hypothyroidism; low FT4 is observed in euthyroid (formerly hypothyroid) patients treated with T3 monotherapy²⁰

In patients continuing on 80 mg MGL-3196 (AUC_{inf} $<$ 5500) who have FT4 LLN ($>$.55 to $<$.7 ng/dL):

At Week 4 or later:

- If FT3 remains normal (not decreased to $<$ LLN) and TSH remains normal, the patient does not have symptoms of hypothyroidism, the patient may continue on the current dose.
- Down titration to 60 mg may be made at the next visit, Week 8 or later if FT4 $<$ LLN ($>$.55 to $<$.7 ng/dL), FT3 and TSH are normal, and there is evidence that the decrease in FT4 $<$ LLN ($>$.55 to $<$.7 ng/dL) is drug-related including a $>$ 30% decrease from baseline in FT4, an increase in SHBG $>$ 120% from baseline and predose exposure $>$ 40 ng/ml for MGL-3196 and $>$ 40 ng/ml for MGL-3196-M1 that is consistent with increased drug exposure relative to the Week 2 PK assessment.

In patients downtitrated to 60 mg at Week 4 who have FT4 LLN ($>$.55 to $<$.7 ng/dL):

- At Week 8 or later, if FT3 and TSH remain normal, the patient does not have symptoms of hypothyroidism, the patient may continue on the current dose.
- Down titration to 60 or 40 mg may be made at the next visit, Week 12 or later if FT4 $<$ LLN ($>$.55 to $<$.7 ng/dL), FT3 and TSH are normal, and there is evidence that the decrease in FT4 $<$ LLN ($>$.55 to $<$.7 ng/dL) is drug-related including a $>$ 30% decrease from baseline in FT4, an increase in SHBG $>$ 120% from baseline and predose exposure $>$ 40 ng/ml for MGL-3196 and $>$ 40 ng/ml for MGL-3196-M1 that is consistent with increased drug exposure relative to the Week 2 PK assessment.

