If these conditions are not met, the patient will continue on current dose and thyroid indices reassessed at subsequent visits. Any randomized patients previously downtitrated based on LLN FT4 per Protocol Amendment 2 who did not meet these criteria for downtitration (Amendment 3) will be returned to the previous dose in a blinded fashion at the next visit.

If FT4 is \leq .55 ng/dL on 80 or 60 mg dose with normal FT3 and TSH (which are unblinded to study personnel for all patients), even if the decrease in FT4 is not felt to be primarily drug-related, a down titration to 60 or 40 mg, respectively, may be made at the next visit as determined by Sponsor and Medical Monitor after blinded review. If it is determined after blinded review by Sponsor and Medical Monitor that thyroid therapy should be initiated, because thyroxine cannot be initiated without breaking the blind, the patient will be discontinued from the study and Early Termination assessments will be performed.

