For patients whose combined estimated $AUC_{(0-24)}$ at 2 weeks at the 80 mg dose is ≤ 3000 ng*hr/ml the dose will be increased to 100 mg at the 4 Week visit, as based on a conservative estimates, the predicted exposure at 100 mg will be significantly ≤ 5500 ng*hr/ml. This prediction is based on data obtained in healthy volunteers in which there is greater than dose proportionate increase in MGL-3196 between 80 and 100 mg daily doses, and less than dose proportionate increases in MGL-3196-M1 between 80 and 100 mg doses. Pharmacokinetic data (blinded to patient ID) obtained from the first 21 patients randomized to MGL-3196 suggest that there are no clear differences in MGL-3196 or MGL-3196-M1 exposure at the 80-mg dose between healthy volunteers and NASH patients enrolled in this study.

For the patients who are relatively early in the Main Study (at week 24 or earlier), if their current dose is 100 mg, their Main Study Week 2 predose MGL-3196 PK value < 5 ng/mL and their Main Study Week 2 $AUC \leq 2500$ ng*hr/mL, then their dose will be increased to 120 mg during the Main study and continued on 120 mg if they meet eligibility criteria for the extension study.

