- Down-titration to 60 mg may be made at the next visit, Week 8 or later if FT4  $<LLN$  ( $>.55$  to  $<.7$  ng/dL), FT3 and TSH are normal, and there is evidence that the decrease in FT4  $<LLN$  ( $>.55$  to  $<.7$  ng/dL) is drug-related including a  $>30\%$  decrease from baseline in FT4, an increase in SHBG  $>120\%$  from baseline and predose exposure  $>40$  ng/ml for MGL-3196 and  $> 40$  ng/ml for MGL-3196-M1 that is consistent with increased drug exposure relative to the Week 2 PK assessment.

In patients down-titrated to 60 mg at Week 4 who have FT4 LLN ( $>.55$  to  $<.7$  ng/dL):

- At Week 8 or later, if FT3 and TSH remain normal, the patient does not have symptoms of hypothyroidism, the patient may continue on the current dose.
- Down-titration to 60 or 40 mg may be made at the next visit, Week 12 or later if FT4  $<LLN$  ( $>.55$  to  $<.7$  ng/dL), FT3 and TSH are normal, and there is evidence that the decrease in FT4  $<LLN$  ( $>.55$  to  $<.7$  ng/dL) is drug-related including a  $>30\%$  decrease

from baseline in FT4, an increase in SHBG >120% from baseline and predose exposure >40 ng/ml for MGL-3196 and > 40 ng/ml for MGL-3196-M1 that is consistent with increased drug exposure relative to the Week 2 PK assessment.

If these conditions are not met, the patient will continue on current dose and thyroid indices reassessed at subsequent visits. Any randomized patients previously down-titrated based on LLN FT4 per Protocol Amendment 2 who did not meet these criteria for down-titration (Amendment 3) will be returned to the previous dose in a blinded fashion at the next visit.

If FT4 is  $\leq .55$  ng/dL on 80 or 60 mg dose with normal FT3 and TSH (which are unblinded to study personnel for all patients), even if the decrease in FT4 is not felt to be primarily drug-related, a down titration to 60 or 40 mg, respectively, may be made at the next visit as determined by Sponsor and Medical Monitor after blinded review. If it is determined after blinded review by Sponsor and Medical Monitor that thyroid therapy should be initiated, because thyroxine cannot be initiated without breaking the blind, the patient will be discontinued from the study and Early Termination assessments will be performed.

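### The main-study dose rules conflict on the top dose, on the criterion for reaching it and on one FT4 step, and must be reconciled

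*Protocol*

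**What the plan says.** **Top dose.** The Synopsis (Dosage Forms and Route of Administration) states that "the dose may be adjusted between 40 and 100 mg in intervals of 20 mg". Protocol 3.1.2 describes doses of 40, 60, 80 and 100 mg. Protocol 5.5.3 refers to 3.1.2 for dose changes and says that the web system assigns drug accordingly.

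Protocol 8.1 goes higher. For patients on 100 mg at Week 24 or earlier who meet its criteria, "then their dose will be increased to 120 mg during the Main study". The dose tables in the Synopsis (Extension Study) and in Protocol 3.1.3 also contain a step from 100 to 120 mg, and their titles and action columns cover the main study. SAP 3.6 mentions 80, 100, 60 and 40 mg for the main study, but not 120 mg.

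**Criterion for 120 mg.** Protocol 8.1 requires a Week 2 combined AUC of at most 2500 ng*hr/ml and a predose level below 5 ng/ml. The two tables require an AUC of at most 3000 ng*hr/ml with the same predose limit.

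**FT4 step.** Protocol 3.1.2 introduces a rule with "In patients downtitrated to 60 mg at Week 4 who have FT4 LLN" and then says "Down titration to 60 or 40 mg may be made at the next visit, Week 12 or later if FT4" is below the lower limit and further conditions hold. The Synopsis has the same text, and SAP 2.2 has "Down-titration to 60 or 40 mg may be made at the next visit, Week 12 or later if FT4".

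**Exposure ceiling.** The Synopsis, Protocol 3.1.2 and SAP 2.2 allow the increase to 100 mg for patients "predicted to have exposure at 100 mg that remains" at or below 5550. Protocol 8.1 and SAP 2.3.2 give 5500 ng*hr/ml for the same prediction.

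**The concern.** These are live instructions. Unblinded staff and the drug-assignment system act on them while everyone else is blinded, so an ambiguous rule is unlikely to be noticed at a site. If two sections give different doses to the same patient, the dose given depends on which section was read or programmed. That bears on safety, and it weakens any later description of who received which dose and why.

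A rule that calls an unchanged dose a down titration also fails to say what should happen to a patient who meets every condition for a drug-related fall in FT4.

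**Working it through.** The plan states no figure to reproduce here. The check sets the current passages side by side, with a little arithmetic on size. The amendment summaries are not used.

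**1. Top dose and its criterion**

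| Place | Highest main-study dose | Week 2 AUC for 120 mg (ng*hr/ml) |
|---|---|---|
| Synopsis, Dosage Forms | 100 mg | none |
| Protocol 3.1.2 (via 5.5.3) | 100 mg | none |
| Synopsis dose table | 120 mg | at most 3000 |
| Protocol 3.1.3 dose table | 120 mg | at most 3000 |
| Protocol 8.1 | 120 mg | at most 2500 |
| SAP 3.6 | 100 mg | none |

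Take a main-study patient at or before Week 24, on 100 mg, with predose below 5 ng/ml.

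- AUC 2500 or less: Section 8.1 and the tables give 120 mg. The Dosage Forms sentence and 3.1.2 provide nothing above 100 mg.
- AUC 2501 to 3000: the tables give 120 mg. Section 8.1 does not. The Dosage Forms sentence and 3.1.2 again stop at 100 mg.

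The gap between the criteria is not marginal. Patients raised to 100 mg at Week 4 were selected for an AUC of at most 3000 (3.1.2 and 8.1). For them the tables' limit of 3000 excludes nobody, whereas 2500 can.

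*Size.* Section 3.1.2 puts patients at or below 3000 at about 10%. Planned active patients: 117 × 2/3 = 78. Then 0.10 × 78 = 7.8, or about 8. The documents do not say how many lie between 2501 and 3000, so the number caught by the AUC conflict is between 0 and about 8.

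*Do the capsules settle it?* A dose is one capsule from each of two bottles, in 40 mg, 60 mg or placebo. The possible non-zero totals are 40, 60, 80 (40 + 40), 100 (40 + 60) and 120 mg (60 + 60). All can be made up, so the supply does not decide between 100 and 120 mg.

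**2. FT4 step**

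- The rule for patients continuing on 80 mg names one lower dose.
- The rule for FT4 at or below .55 ng/dL names two starting and two ending doses and pairs them: "a down titration to 60 or 40 mg, respectively, may be made at the next visit".
- The disputed rule covers one group, those reduced to 60 mg at Week 4, yet names two ending doses without pairing them. For a patient still on 60 mg, 60 to 60 is no change.

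**3. Exposure ceiling**

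- Difference: 5550 − 5500 = 50, and 50/5500 = 0.9%.
- Entry threshold for 100 mg: AUC of at most 3000 on 80 mg. Linear scaling gives 3000 × 100/80 = 3750, below both ceilings.
- Rise needed to reach a ceiling: 5500/3000 = 1.83-fold or 5550/3000 = 1.85-fold, for a dose increase of 100/80 = 1.25-fold.

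Linear scaling is an assumption. Section 8.1 says that the parent drug rises more than in proportion to dose between 80 and 100 mg, and the metabolite less. Even so, the two ceilings would rarely separate patients.

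**The case against.** The strongest reply is that this is editorial clean-up with little practical effect. Much of that stands, and it limits the point in four ways.

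- **The Synopsis does not set a firm 100 mg maximum.** A reader might infer that Section 8.1 breaches a Synopsis limit by 20%. The Synopsis contains its own table with the 120 mg step, so it contradicts itself. The Dosage Forms sentence may simply not have been updated.
- **The FT4 heading does not exclude every other current dose.** It describes what happened at Week 4, while the action comes at Week 12 or later. The dose tables let a 60 mg patient return to 80 mg, and such a patient could later step to 60. The route is narrow: the increase needs a Week 8 predose below 1 ng/ml and SHBG below +75%, whereas the FT4 rule needs a predose above 40 ng/ml and SHBG above 120%. The rule does not mention this case.
- **The FT4 rule appears to have been little used.** The Synopsis and 3.1.3 report no need so far for FT4 down titrations. The same sentence, however, carries the rules into the extension.
- **The dose summary would not be corrupted by a 60-to-60 event.** SAP 3.6 tabulates the dose taken at each visit, so that patient is counted at 60 mg, correctly.

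It is also fair that Section 8.1 uses 5500 to justify the 100 mg step and not as a second selection test.

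None of this removes the different dose outcomes for a patient on 100 mg, or the tie in 5.5.3 to a section that omits 120 mg.

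**Conclusion.** The conflicts are real and lie in current text. In order of weight:

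1. The top main-study dose is 100 mg in some places and 120 mg in others, and the AUC criterion for 120 mg is 2500 or 3000 ng*hr/ml. This changes the dose for identifiable patients. The AUC conflict touches at most about 8, assuming the planned 78 active patients and the protocol's own rough 10%.
2. The FT4 rule offers an option that is no reduction for a patient still on 60 mg. Use so far appears small, and the number affected is not given.
3. The ceiling of 5550 against 5500 differs by 0.9% and would rarely change who is increased.

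A reader might infer that the efficacy result is at risk. The documents do not support that for the primary comparison: the model in SAP 3.7.2.1 compares all active patients with placebo, whatever their dose. The consequence for analysis is narrower. SAP 3.6 describes a main-study dose set without 120 mg, although its tabulation by dose could include it. The SAP introduction cites protocol Amendment 4, which may explain the gap.

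This review takes no view on which dose, criterion or ceiling is right.

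**What to change.** Reconcile the Synopsis, Protocol 3.1.2, 3.1.3, 5.5.3 and 8.1, and SAP 2.2, 2.3.2 and 3.6, so that there is:

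- one main-study dose range;
- one AUC criterion for the step to 120 mg;
- one outcome per current dose in the FT4 rule;
- one ceiling on predicted exposure at 100 mg.

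Protocol 8.2 repeats the limit of 2500 for the extension and should be checked in the same pass. Section 5.5.3 should point to every section that can change a dose. SAP 3.6 should list every dose allowed in the main study.

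The sponsor and DSMB make the clinical choices. If dosing under a rule has already finished, the clinical study report should state which passage was applied and to how many patients.

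The cost is wording in a protocol amendment and a SAP revision, plus a check that the web system matches. No new data, sample size or analysis model is needed.

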**Either predose<15ng/ml plus 4h<600ng/ml OR SHBG<+75%CFB.

No titrations will be made based on TSH which has not changed in the Main Study. TSH will be unblinded in the Extension Study. Downtitrations have not been needed for changes in FT4, but the same downtitration rules will apply in the Extension Study.

At the Extension Study Week 12 Visit, patients will have an MRI-PDFF. Within 10 days prior to or at the Extension Study Week 36 visit while the patient is still on treatment another MRI-PDFF will be performed. If available, a fibroscan may be performed at the Extension Study Week 36 visit.

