4.2 Exclusion Criteria

Note: Unless otherwise specified, repeat testing may be performed in consultation with the Medical Monitor.

Patients who meet any of the following criteria will be excluded from participation in the study:

1. History of significant alcohol consumption for a period of more than 3 consecutive months within 1 year prior to screening;

Note: Significant alcohol consumption is defined as average of >20 g/day in female patients and >30 g/day in male patients;

2. Inability to reliably quantify alcohol consumption based upon judgment of the Investigator;

3. Use of drugs historically associated with NAFLD (amiodarone, methotrexate, systemic glucocorticoids, tetracyclines, tamoxifen, estrogens at doses greater than those used for hormone replacement, anabolic steroids, valproic acid, and other known hepatotoxins) for more than 2 weeks in the year prior to screening;
4. Hyperthyroidism;
5. Patients on thyroid replacement therapy or with untreated clinical or subclinical hypothyroidism;

Note: If TSH is up to 1.5 x ULN on screening with normal free T4, one repeat test is allowed to confirm the elevation in TSH. If TSH and free T4 are normal upon repeat testing, patient may be included. Patients with a history of thyroid hormone replacement therapy or patients who have discontinued thyroid hormone replacement therapy (including thyroxine) ≥ 2 months prior to randomization may be included in the study if this criterion is met;

During the study, patients who have elevated levels of TSH > 7 IU/ml on at least two separate consecutive visits and are symptomatic of hypothyroidism, or TSH > 10 IU/ml, who are indicated to be on thyroxine for clinical hypothyroidism, may initiate treatment with low doses of thyroxine consistent with American Thyroid Association guidelines, with frequent monitoring of TSH levels at Study Visits (and within 2 weeks of initiation of thyroxine), safety labs, and monitoring of other symptoms related to hyper or hypothyroidism. Thyroxine may be administered at $\frac{1}{4}$ to $\frac{1}{2}$ the anticipated dose (a starting dose of 25 ug per day) with careful monitoring of TSH levels and symptoms related to hyper or hypothyroidism, with increments in thyroxine dose after no less than 4-6 weeks.

NOTE: It is anticipated that initiation of thyroxine therapy will occur very infrequently during the study and 50-75 ug thyroxine replacement will suffice for most patients requiring thyroxine treatment.

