5.6 Prior and Concomitant Medications and/or Procedures

5.6.1 Excluded Medications

Excluded medications include:

- Triiodothyronine (liothyronine [Cytomel®]);
- Thyroxine (excluded at time of randomization), and very infrequently used during the study, in that thyroxine therapy may be initiated in patients who become clinically hypothyroid during the study as described in exclusion criteria #5;

Note: Patients who discontinue thyroxine ≥ 2 months prior to randomization may be included in the study, as described, during the study thyroxine therapy may be initiated;

- Obeticholic acid, ursodeoxycholic acid (Ursodiol® and Urso®), high dose vitamin E (>400 IU/day) except as permitted in exclusion criteria #10, or pioglitazone within 90 days prior to enrollment or since screening biopsy, whichever is longer;
- Use of the following lipid-modifying therapies: fibrates except for fenofibrate taken at night for at least 2 weeks prior to randomization and during the study, niacin, proprotein convertase subtilisin/kexin type 9 inhibitors, bile acid sequestrants, and statins except as permitted in the exclusion criteria #9;
- Major inhibitors of organic anion-transporting polypeptide transporters such as gemfibrozil, cyclosporine A, or protease inhibitors;
- Use of drugs historically associated with NAFLD (amiodarone, methotrexate, systemic glucocorticoids, tetracyclines, tamoxifen, estrogens at doses greater than those used for hormone replacement, anabolic steroids, valproic acid, and other known hepatotoxins) Drugs with known liver toxicity;
- Repaglinide or a glitazone such as rosiglitazone (substrates of cytochrome P₄₅₀ 2C8 [CYP2C8] or gemfibrozil [inhibitor of CYP2C8]);
- Chronic use of oral corticosteroids unless discontinued 3 months before screening. Addition of oral corticosteroids during the study except short term low dose < 1 week taper is not allowed. This exclusion does not include topical corticosteroids, or corticosteroid injections in muscle or joint;
- Warfarin treatment; and
- Any medications with the potential to affect thyroid hormone production and/or that may interfere with thyroid function including but not limited to methimazole, PTU, tyrosine kinase inhibitors, iodide, and glucocorticoids. Unless, for example, in the case of lithium, the medication is stably dosed and thyroid hormone levels are normal.

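### Protocol 3.1.2 and SAP 2.2 remove a patient who needs thyroxine, while Exclusion #5 and 5.6.1 let such a patient start it and stay, and nothing says which rule governs

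*Protocol*

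**What the plan says.** Two sets of current passages deal with starting thyroxine after randomisation.

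**Removal.** Protocol 3.1.2 first allows a dose reduction when FT4 is at or below 0.55 ng/dL "with normal FT3 and TSH (which are unblinded to study personnel for all patients". It then says that if the sponsor and medical monitor decide on blinded review that thyroid therapy is needed, "because thyroxine cannot be initiated without breaking the blind, the patient will be discontinued from the study". The Treatment Period text of the Synopsis carries the same rule, as does SAP 2.2 ("thyroid therapy should be initiated, because thyroxine cannot be initiated without breaking the blind").

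**Treatment with retention.** Exclusion #5 in Protocol 4.2, repeated in the Synopsis, concerns patients whose TSH rises during the study: above 7 on two consecutive visits with symptoms, or above 10, with thyroxine indicated for clinical hypothyroidism. These patients "may initiate treatment with low doses of thyroxine consistent with American Thyroid Association guidelines". The text adds TSH checks at study visits and later dose increments, so the patient is plainly meant to stay. Section 5.6.1 agrees: "thyroxine therapy may be initiated in patients who become clinically hypothyroid during the study as described in exclusion criteria #5". Neither passage mentions unblinding or discontinuation.

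The Synopsis contains both rules. No passage says which one governs.

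**The concern.** One set of passages says thyroxine cannot be started in this trial without breaking the blind. The other sets out how to start it in a blinded trial. As general statements they cannot both hold, and a site has no text telling it which to follow.

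The first stake is patient management: a hypothyroid patient is either treated and followed within the study or taken out of it. The second is the data. A patient withdrawn after Week 12 may have no Week 36 biopsy and no Week 36 MRI-PDFF, and some of the Week 36 analyses need them.

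**Working it through.** No arithmetic applies, because the documents give no rate of thyroxine starts. The check sets the passages side by side and asks which patients each one reaches.

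**1. Inputs**

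| | Protocol 3.1.2, Synopsis, SAP 2.2 | Exclusion #5 (4.2, Synopsis), 5.6.1 |
|---|---|---|
| Context | Paragraph on FT4 at or below 0.55 ng/dL with FT3 and TSH normal | Raised TSH, thyroxine indicated for clinical hypothyroidism |
| Condition in the operative sentence | Sponsor and medical monitor decide thyroid therapy is needed; no TSH limit | TSH above 7 twice with symptoms, or above 10 |
| Action | Discontinue; Early Termination assessments | Start low-dose thyroxine; monitor at study visits |
| Reason or safeguard | Starting would break the blind | Monitoring of TSH, safety laboratory tests and symptoms; blind not mentioned |

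**2. Which patients fall under which rule**

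- *FT4 at or below 0.55, TSH normal.* Only 3.1.2 applies. There is no conflict.
- *TSH above 10, thyroxine indicated, FT4 above 0.55.* Exclusion #5 says start and stay. Section 3.1.2 is silent if its removal sentence is confined to its paragraph. It says discontinue if the stated reason is taken at its word.
- *FT4 at or below 0.55, TSH later above 10.* Exclusion #5 says start and stay. The patient came under review through the 3.1.2 paragraph, whose removal sentence does not drop away when TSH rises. Both rules can be read to apply.

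**3. Test of the reason.** Suppose starting thyroxine does break the blind. Then Exclusion #5 and 5.6.1 cannot operate as written in a double-blind study. Suppose it does not. Then the reason given in 3.1.2 is wrong as a general statement and supports removal only if it is limited to some subset of patients. Either way one passage needs changing.

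**4. Who the removal sentence most naturally concerns.** Section 3.1.2 itself states that low FT4 with normal FT3 and TSH does not indicate hypothyroidism. A decision that thyroid therapy is needed would therefore usually concern a patient with raised TSH, which is the Exclusion #5 patient.

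**5. What removal does to the data**

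- SAP 3.7.2.5: the observed-case Week 36 MRI-PDFF analysis includes only patients who finish that scan. A second analysis carries the last observation forward for those who withdraw between Weeks 12 and 36.
- SAP 3.7.3: the biopsy mITT set needs eligible biopsies at both baseline and Week 36.
- Protocol 6.6 lists MRI-PDFF and, in the main study, biopsy at early termination, but leaves some procedures to discretion. Section 9.15 leaves the early-termination biopsy to the investigator.

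Removal can therefore cost Week 36 biopsy and observed-case MRI-PDFF data, but does not do so automatically.

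**The case against.** The best defence is that the two rules cover different patients. The removal sentence closes a paragraph about low FT4 with normal TSH, while Exclusion #5 needs raised TSH. The reason about the blind can also be confined to that paragraph: it describes FT3 and TSH as visible to study personnel and does not say so of FT4, so acting on an FT4 signal might reveal allocation where acting on a visible TSH would not. The patient whose TSH later exceeds 10 also no longer meets the paragraph's opening condition.

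This narrows the overlap but does not remove it. The documents never state that limit, the removal sentence repeats no TSH condition, and its reason is worded for thyroxine in general.

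The defence also limits the consequences, and that part stands. Last-observation-carried-forward keeps a withdrawn patient in one Week 36 MRI-PDFF analysis. SAP 3.1 accepts scans and biopsies up to three weeks after the last dose, and the Liver Biopsy Evaluable Population (SAP 3.2.4) asks only for a post-treatment biopsy.

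A reader might infer more than the documents support:

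- *That the text contradicts itself on who sees TSH.* Section 3.1.2 says TSH is visible in the main study, and 3.1.3 says "TSH will be unblinded in the Extension Study". Both can be true.
- *That a permitted start counts as prohibited medication.* Section 5.6.1 limits the thyroxine exclusion to the time of randomisation and then allows later starts. Withdrawal under 4.3 is optional.
- *That the active arm would lose a definite number of patients.* No rate is given. Section 3.1.3 reports TSH unchanged and no dose reductions needed for FT4 in the main study. Exclusion #5 starts are led by TSH, and nothing indicates they would be one-sided.
- *That the Week 12 primary result is at risk.* The Amendment 6 rationale reports that readout as already obtained in 116 patients.

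**Conclusion.** The inconsistency is real and stands in current text. Protocol 3.1.2, the Synopsis and SAP 2.2 point to removal, Exclusion #5 and 5.6.1 point to treatment with retention, and no passage ranks them. The conclusion rests on reading the removal sentence as worded, without a TSH limit that the documents do not supply.

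The size cannot be computed. Starts are expected very infrequently, so the effect on any Week 36 comparison is probably very small, and the point does not threaten the trial's conclusions. It deserves correction because it gives opposite instructions for managing and retaining a patient and is cheap to settle. No view is taken here on which clinical rule is right.

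It would be too strong to say that SAP 3.7.4.3 formally tests thyroid values altered by replacement. That section gives summary statistics for the thyroid hormones and names an ANCOVA only for Reverse T3.

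**What to change.** - Reconcile Protocol 3.1.2, the matching Synopsis text and SAP 2.2 with Exclusion #5 (4.2 and Synopsis) and 5.6.1, so that one consistent rule covers every thyroxine start. The sponsor and medical monitors choose the rule.
- Correct the statement that thyroxine cannot be started without breaking the blind or, if it was meant only for the low-FT4, normal-TSH case, say so.
- Optionally, flag thyroid values taken after a thyroxine start in the SAP 3.7.4.3 summaries.

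The cost is one protocol clarification, the matching edit in SAP 2.2 and, if wanted, one more SAP sentence. No new data, visits or patients are needed.
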